4 STATISTICAL METHODOLOGY

4.1 General Methodology

The descriptive statistics of continuous variables will be given as Mean, standard deviation (SD), Median, Q1, Q3, Minimum, Maximum and 95% CIs. The distribution of categorical and dichotomous variables will be given as number and percentage.

Statistical tests will be performed for Functional gain (PTA-4 and frequencies), difference in speech recognition score between unaided and aided (AB[s] short list test for SSD patients), effective gain (PTA-4 and frequencies), and GBI scores (from before and after fitting).

Continuous data will be tested for normality using the Shapiro-Wilk test. Paired t-test will be performed if the data is normally distributed. Wilcoxon signed-rank test will be performed if the data is not normally distributed. For categorical change variables i.e. change <0, 0 and >0 sign test will be used to test whether the change is significant or not. Pearson's correlations (or Spearman's if the data is not normally distributed) will be used to test correlations.

All tests will be two-tailed and conducted at 0.05 significance level. All analyses will be performed by using SAS® v9.4 (Cary, NC).

All analyses will be performed on the ITT population and the Target populations (TP1 and TP2) where applicable. Subgroup analyses (combined group (CHL/MHL+SSD and SNHL if any) and the subgroups CHL/MHL & SSD) will be conducted for the ITT population. Additional analyses will be performed on one subset of the TP1:

- Bilaterally fitted Ponto 3 SuperPower users with CHL/MHL. This is to avoid any contribution from the non-Ponto 3 SuperPower fitted ear in unilaterally fitted users or bimodally users (BAHS on one ear, hearing aid on the other), since all measurements have been performed without masking or blocking of the contralateral ear.

An overview of the analysis per objective is presented in the table below.

Objectives	ITT	Target	Effect of Ponto 3 SuperPower (bilaterally fitted CHL/MHL subjects)
A	X	X (TP1)	X
B	X	X (TP1)	X
C	X	X (TP1)	X
D	X	X (TP2)	
E	X	X (TP1)	X
F	X	X (TP1)	X
G	X	X (TP1 + TP2)	
H	X	X (TP1 + TP2)	X

STATISTISKA KONSULTGRUPPEN			Statistical Analysis Plan	
Protocol: Investigating hearing with Ponto 3 SuperPower, a bone anchored hearing aid - Investigating hearing with Ponto 3 SuperPower, a bone anchored hearing solution.				Protocol No: BC107
			Version: 1.0	Page 13 of 23

I	X	X (TP1)	
J	X	X (TP1 + TP2)	

The additional analysis on the connectivity devices will be conducted on the ITT population.

Generally, PTA4 (for functional gain, effective gain, air-to-bone gap, aided sound field audiology, AC- and BC audiology and BC in-situ measurements) will be calculated as the mean value of all non-missing values. Sensitivity analyses will be made for patients where all four including frequencies are non-missing.

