#### 9.3.3.1 Collection of Pure tone thresholds from audiogram measured prior to fitting of Ponto 3 SuperPower

Unmasked and if available masked BC thresholds for frequencies 500 Hz, 1kHz and 2 kHz and AC thresholds for frequencies 250 Hz, 500Hz, 1kHz, 2 kHz, 3kHz, 4kHz, 6kHz and 8kHz will be collected from audiogram obtained prior to Ponto 3 SuperPower were fitted.

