#### 9.3.3.2 Collection of BC In-situ thresholds from BC In-situ audiogram measured during fitting of Ponto 3 SuperPower

BC In-situ thresholds for frequencies 250 Hz, 500 Hz, 1 kHz, 2 kHz, 3 kHz, 4 kHz, 6 kHz and 8 kHz will be collected from the BC In-situ audiogram obtained when Ponto 3 SuperPower were fitted.

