Protocol: Investigating hearing with Ponto 3 SuperPower, a bone anchored hearing aid - Investigating hearing with Ponto 3 SuperPower, a bone anchored hearing solution.	Protocol No: BC107	Version: 1.0
		Page 3 of 23

7.1	Listing of Tables	15
7.2	Listing of Figures	18
7.3	Listing of Listings.....	23

STATISTISKA KONSULTGRUPPEN		Statistical Analysis Plan
Protocol: Investigating hearing with Ponto 3 SuperPower, a bone anchored hearing aid - Investigating hearing with Ponto 3 SuperPower, a bone anchored hearing solution.	Protocol No: BC107	Version: 1.0
		Page 4 of 23

LIST OF ABBREVIATIONS

Abbreviation	Definition
AC	Air conduction
ANOVA	Analysis of variance
BAHS	Bone-anchored hearing system
BC	Bone conduction
CHL	Conductive hearing loss
CI	Cochlear implant
CIP	Clinical Investigational Plan
DB	Database
dB	Decibel
DD	Device deficiency
GBI	Glasgow Benefit Inventory
HA	Contralateral hearing aid
ITT	Intent-to-Treat
Max	Maximum
MHL	Mixed hearing loss
Min	Minimum
MOM	Minutes Of Meeting
NR	Noise reduction
P3SP	Ponto 3 SuperPower
PP	Per-Protocol
PTA3	Pure tone average, calculated on average for frequencies 500, 1000 and 2000 Hz
PTA4	Pure tone average, calculated on average for frequencies 500, 1000, 2000 and 4000 Hz
SD	Standard deviation
SSD	Single sided deafness

STATISTISKA KONSULTGRUPPEN		Statistical Analysis Plan	
Protocol: Investigating hearing with Ponto 3 SuperPower, a bone anchored hearing aid - Investigating hearing with Ponto 3 SuperPower, a bone anchored hearing solution.		Protocol No: BC107	Version: 1.0 Page 5 of 23

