2 STUDY POPULATIONS

2.1 Definition of Study Populations

Due to the retrospective design, no safety population will be defined for the study. The intention-to-treat (ITT) population will include all subjects included in the study. No per-protocol (PP) population will be defined as this study collects data retrospectively and thus the expectation is that not all data for the described procedures will be available for all patients. Instead, the ITT population will be divided into two separate target groups depending on the type of hearing loss in the subjects.

The decision of the populations will be made prior to DB lock and information regarding each patient's population belonging will be found in the DB lock MOM.

The Target populations (TPs) are defined as:

- TP1: Subjects with conductive or mixed hearing losses (within intended use for Ponto 3 SuperPower): pure tone average (PTA3) bone conduction (BC) threshold on the BAHS(s) ear(s) better than or equal to 65 dB HL, based on BC threshold when Ponto 3 SuperPower were fitted.

STATISTISKA KONSULTGRUPPEN		Statistical Analysis Plan	
Protocol: Investigating hearing with Ponto 3 SuperPower, a bone anchored hearing aid - Investigating hearing with Ponto 3 SuperPower, a bone anchored hearing solution.		Protocol No: BC107	Version: 1.0 Page 8 of 23

- **TP2:** Subjects with single sided deafness (SSD) (within intended use for Ponto 3 SuperPower): pure tone average air conduction (AC) threshold of the hearing ear being better than or equal to 20 dB HL AC (measured at 0.5, 1, 2 and 3 kHz). In case AC is larger than 20 dB HL then the patients must not use a hearing aid on the other side.

Additional analyses will be performed on one subset of the TP1:

- Bilaterally fitted Ponto 3 SuperPower users with CHL/MHL. This is to avoid any contribution from the non-Ponto 3 SuperPower fitted ear in unilaterally fitted users or bimodally users (BAHS on one ear, hearing aid on the other), since all measurements have been performed without masking or blocking of the contralateral ear.

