- Effective gain with Ponto 3 SuperPower, i.e. the difference between aided sound field thresholds and the BC In-situ thresholds on the aided ear(s) measured when the Ponto 3 SuperPower(s) was fitted. The effective gain is calculated as the average (PTA4) of frequencies 500, 1000, 2000 and 4000 Hz for patients with CHL/MHL (ITT_{CHL/MHL} / TP1 / Bilaterally patients) (Objective E). In case of a bilateral Ponto fitting it is BC In-situ thresholds for the best ear, calculating PTA4 for both ears and then choose the best one, that will be used. Average PTA4 across patients should be reported and computed for all the patients, and for only individuals where all four frequencies (500, 1000, 2000 and 4000 Hz) are non-missing. The latter PTA4 should be used for the figures. Used in sensitivity analyses.
- Effective gain is defined as the difference between aided sound field thresholds measurement with Ponto 3 SuperPower(s) and BC In-situ thresholds at the time when the Ponto 3 SuperPower was fitted. The effective gain is calculated for each frequency: 500, 1000, 2000 and 4000 Hz for patients with CHL/MHL (ITT_{CHL/MHL} / TP1 / Bilaterally patients) (Objective F). In case of a bilateral Ponto fitting it is BC In-situ thresholds for the best ear, calculating PTA4 for both ears and then choose the best one, that will be used.
- Glasgow Benefit Inventory (GBI) scores (ITT / TP1 / TP2) (Objective G). Presented per before and after fitting of Ponto 3 SuperPower for:

STATISTISKA KONSULTGRUPPEN		Statistical Analysis Plan	
Protocol: Investigating hearing with Ponto 3 SuperPower, a bone anchored hearing aid - Investigating hearing with Ponto 3 SuperPower, a bone anchored hearing solution.		Protocol No: BC107	Version: 1.0 Page 11 of 23

- Total score
- General subscale
- Social support subscale
- Physical health
- The difference between masked (if not available unmasked) BC and AC thresholds, denoted 'air to bone gap', calculated as the average (PTA3) of frequencies 500, 1000 and 2000 Hz and for each frequency, from audiogram measured in connection with the fitting of Ponto 3 SuperPower for patients with CHL/MHL (ITT_{CHL/MHL} / TP1) (Objective I). In case of a bilateral Ponto fitting it is the best ear, calculating PTA3 for both ears and then choose the best one, that will be used. PTA3 will be calculated as the mean value of all non-missing values. A sensitivity (variable) analysis will be made for patients where all four including frequencies are non-missing.

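### The SAP's sensitivity analysis for audiogram bone conduction and the air-to-bone gap requires four frequencies, but audiogram BC is collected at three, so no subject can qualify as written; the PTA3/PTA4 label is also inconsistent

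*SAP*

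**What the plan says.** The SAP's list of abbreviations defines two averages. PTA4 covers 500, 1000, 2000 and 4000 Hz. PTA3 is "Pure tone average, calculated on average for frequencies 500, 1000 and 2000 Hz".

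Protocol 9.3.3.1 limits the audiogram BC data to three frequencies: "Unmasked and if available masked BC thresholds for frequencies 500 Hz, 1kHz and 2 kHz". The in-situ BC measurement made at fitting is separate and wider: "BC In-situ thresholds for frequencies 250 Hz, 500 Hz, 1 kHz, 2 kHz, 3 kHz, 4 kHz, 6 kHz and 8 kHz" (Protocol 9.3.3.2).

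SAP 3.2.2 defines the air-to-bone gap for objective I as "calculated as the average (PTA3) of frequencies 500, 1000 and 2000 Hz and for each frequency". It takes the mean of the non-missing values and then states: "A sensitivity (variable) analysis will be made for patients where all four including frequencies are non-missing".

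SAP 4.1 gives a general rule: "Generally, PTA4 (for functional gain, effective gain, air-to-bone gap, aided sound field audiology, AC- and BC audiology and BC in-situ measurements) will be calculated". Only non-missing values enter that average. The restriction follows: "Sensitivity analyses will be made for patients where all four including frequencies are non-missing". Audiogram BC and the gap are both on that list.

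**The concern.** A sensitivity analysis restricted to complete averages has a purpose here. PTA values are built from whatever thresholds are present, and SAP 4.2.1 treats a threshold that could not be measured (code 999, used for sound field, AC and BC) as missing. A subject's average can therefore rest on fewer frequencies than its name implies, and the complete-frequency analysis is the check on that. For audiogram BC and the gap, the stated condition asks for a frequency that the protocol does not collect. A programmer following the text would get no subjects, or would have to reinterpret the rule once data are in hand.

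The labels add to the ambiguity. Some table titles put a three-frequency BC mean under the same name as a true four-frequency AC mean, while the figures call the BC mean PTA3.

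**Working it through.** The plan states no sample size for this sensitivity set, so there is no figure to reproduce. The check is whether each measure's collected frequencies contain the four that PTA4 needs. A difference between two measures can be formed only at frequencies they share.

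| Measure | Source | Frequencies (Hz) | All of 500, 1000, 2000, 4000? |
|---|---|---|---|
| AC audiogram | Protocol 9.3.3.1 | 250, 500, 1000, 2000, 3000, 4000, 6000, 8000 | Yes |
| BC audiogram | Protocol 9.3.3.1 | 500, 1000, 2000 | No, 4000 absent |
| BC in-situ | Protocol 9.3.3.2 | 250, 500, 1000, 2000, 3000, 4000, 6000, 8000 | Yes |
| Aided sound field | Protocol 9.3.3.3 | 500, 1000, 2000, 3000, 4000 | Yes |
| Functional gain | AC audiogram and sound field | 500, 1000, 2000, 3000, 4000 | Yes |
| Effective gain | Sound field and BC in-situ | 500, 1000, 2000, 3000, 4000 | Yes |
| Air-to-bone gap | AC audiogram and BC audiogram | 500, 1000, 2000 | No, 4000 absent |

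**Size of the set.** Under the four-frequency condition, audiogram BC gives 0 of the 55 planned subjects and the gap gives 0. Under a three-frequency condition the ceilings are 55 for audiogram BC and the number of conductive or mixed loss subjects for the gap. The documents do not fix that number. The three strata of about 15 in Protocol 9.1.1 suggest 15 + 15 + 15 = 45, but this is a recruitment aim. The zero does not depend on it.

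**Size of the average.** With 4000 Hz always absent, the mean of non-missing BC values over the four PTA4 frequencies is (BC500 + BC1000 + BC2000) / 3, which is PTA3. The difference is 0 dB, so the BC PTA4 label is wrong but the number is not.

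**Labels side by side.**

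| Quantity | Called PTA4 in | Called PTA3 in |
|---|---|---|
| Audiogram BC average | SAP 3.1.2; SAP 4.1; titles of tables 14A.1.3, 14B.1.2, 14C.1.2 | Figures 14.1.6.2, 14.2.5.2, 14.3.2, 14.4.4.2 |
| Air-to-bone gap | Protocol Table 4 (objective I); SAP 1.1.2; SAP 4.1 | SAP 3.2.2; figures 14.1.6.1, 14.2.5.1, 14.4.4.1 |

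Titles 14A.7 and 14B.5.1 are loosely worded. They name only PTA4, but do not clearly attach it to BC or to the gap. In Protocol Table 4 the objective carries the PTA4 label while its endpoint text lists only the three frequencies.

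**The case against.** The best defence is that the sentence in the objective I text is a carry-over. The same sentence stands in SAP 3.2.1 for functional gain, where four frequencies are right. In 3.2.2 it directly follows a rule for PTA3 on three named frequencies, so a sensible reader would take it to mean all component frequencies. That is probably what was meant, and it limits the weight of the point. It does not remove it, because the text says four in both places. Nor does the word that opens the general rule in SAP 4.1 help. It may let the specific section govern the gap's label, but the specific section repeats the same condition.

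The defence is also right that no listed table or figure title is identified as a sensitivity output for the gap or for audiogram BC. The SAP directs figures to the complete-frequency set only for the primary endpoint (4.6.1) and effective gain (3.2.2). The separate table and figure guideline named in SAP section 7 is not among the documents, so it cannot be said whether it resolves the matter.

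A reader might infer three stronger things that the documents do not support:

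- **The gap estimate is biased.** If the gap were formed as four-frequency AC minus three-frequency BC, it would differ from the PTA3 gap by (AC4000 − AC PTA3) / 4. With AC at 4000 Hz assumed 10, 20 or 30 dB worse than AC PTA3, that is 2.5, 5.0 or 7.5 dB. SAP 3.2.2 defines the gap on 500, 1000 and 2000 Hz, so following it gives a discrepancy of 0 dB.
- **SAP text and tables say PTA4 and figures say PTA3.** SAP 3.2.2 uses PTA3 for the gap. SAP 2.1 uses PTA3 for BC in TP1, although its reference to BC at the time of fitting leaves unclear whether the audiogram or the in-situ measurement is meant. Only three table titles call the BC average PTA4 outright.
- **Effective gain is affected.** It uses in-situ BC, which includes 4000 Hz.

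**Conclusion.** The point holds as a limited internal inconsistency in an operative rule. As written, the sensitivity analyses for audiogram BC and objective I cannot be carried out on the planned data, because the qualifying set is empty. The label for these averages is inconsistent within the SAP and, for the gap, also in the protocol.

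The conclusion rests on the protocol's data-collection list. It would change only if BC at 4000 Hz were recorded outside that list, and the SAP's own figure titles show audiogram BC at three frequencies only.

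The primary endpoint, effective gain, every planned statistical test and the main gap estimate under SAP 3.2.2 are unaffected. The gap is not among the variables SAP 4.1 lists for testing. This is worth correcting because it is cheap and certain on the text; it does not threaten the study's conclusions.

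**What to change.** 1. In SAP 3.2.2 (objective I) and 4.1, state that for audiogram BC and the air-to-bone gap PTA3 is the mean of all non-missing values at 500, 1000 and 2000 Hz, and that the sensitivity analysis uses patients with all three non-missing. SAP 4.1 is the only place that gives the non-missing-mean rule for audiogram BC (3.1.2 says only that nothing is imputed), so the rule must be kept when BC is taken off the PTA4 list.
2. Keep PTA4 and the four-frequency condition for AC, sound field, BC in-situ, functional gain and effective gain.
3. Relabel audiogram BC and the gap as PTA3 in SAP 1.1.2, 3.1.2 and 4.1, and in tables 14A.1.3, 14A.7, 14B.1.2, 14B.5.1 and 14C.1.2, with any matching entries in the table and figure guideline.
4. Relabel objective I in Protocol Table 4 at the next amendment.

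An AC PTA3 row beside BC in the tables would match the figures, which already call for AC PTA3, but it is optional. The cost is minor wording edits to the SAP and five table titles. No new data are needed.

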4.2 Missing Data

Missing data (i.e., single questions, single thresholds) will not be imputed and will be disregarded from the analysis.

4.2.1 Database codings

1. SMART TRIAL codes

The SMART TRIAL codes will be treated as Not A Number (NANs) and will be disregarded from the analysis. Applicable for the BC107 study are:

- .b: Not answered.
- .c: Not answered due to cancel.
- .d: Not answered due to discontinuation in study.
- .e: Not answered due to exclusion.
- .h: Not answered, hidden by show rule(s).
- .n: Marked as 'Answer not available'.
- .ns: Possibility not selected.

2. 999: Data not measurable

The code is used for sound field audiology, AC- and BC thresholds (i.e., if a threshold is not measurable the code '999' must be entered manually by the investigator). The code will be treated as Not A Number (NANs) and will be disregarded from the analysis.

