### **9.3 Clinical Investigation Procedures**

#### **9.3.1 Subject characteristics**

	Title Investigating hearing with Ponto 3 SuperPower, a bone anchored hearing aid	Document no Doc-00072164	Revision 3	Page 13(29)
---	--	------------------------------------	----------------------	-----------------------

The following subject characteristics will be collected:

- Gender
- Age at fitting visit
- Type of hearing/hearing loss on right and left ear (MHL/CHL; SSD and SNHL, normal hearing)
- Type of hearing solution on right and/or left ear
- BAHS surgery, side(s) and year
- Date of Ponto 3 SuperPower fitting on abutment (mm.year)
- Connectivity devices (device: Oticon Medical streamer, ConnectLine Tv adapter, ConnectLine microphone, Connectline phone adapter, usage: )

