3.2.3 Additional Efficacy Variables

- Self-reported usage of connectivity device(s) previously given to the test subject (ITT).

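### SAP 4.2.1 discards the code for an unticked option as if it were missing; tick-list percentages would then read 100% if non-missing counts form the denominator

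*SAP*

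**What the plan says.** SAP 4.2.1 (Database codings) sets the rule for codes exported by the data-capture system: "The SMART TRIAL codes will be treated as Not A Number (NANs) and will be disregarded from the analysis". The list of codes relevant to BC107 has seven entries. Five (.b, .c, .d, .e, .h) are forms of unanswered question, and .n marks an answer that is unavailable. The last is "ns: Possibility not selected". No exception is made for it.

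SAP 4.2 gives the general rule: "Missing data (i.e., single questions, single thresholds) will not be imputed and will be disregarded from the analysis". Protocol 11.4 adds that when a whole variable is missing for a subject, that subject is removed case-wise for that variable.

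The analysis most likely to meet .ns is connectivity. Protocol 9.3.1 collects "Connectivity devices (device: Oticon Medical streamer, ConnectLine Tv adapter, ConnectLine microphone, Connectline phone adapter, usage", with nothing entered after the last word. SAP 3.2.3 defines the variable as "Self-reported usage of connectivity device(s) previously given to the test subject (ITT". On the analysis set, SAP 4.1 says: "The additional analysis on the connectivity devices will be conducted on the ITT population". On the summary, it says: "The distribution of categorical and dichotomous variables will be given as number and percentage". The denominator of that percentage is not given. SAP 7 defers table layout to a separate guideline, which is not among the documents reviewed.

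**The concern.** The .ns code differs in kind from the other six. Those record that no answer is available. The .ns code records that the question offered an option and the option was not chosen. When the question was answered, that is information, and it is the only way a tick-list field records 'no'.

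If .ns is set to missing and missing values are dropped, the 'no' answers leave the data for each option and only the 'yes' answers remain. The resulting percentage says nothing about how common the device is. The error runs in one direction only, upwards, and it would appear in the sponsor's report on accessories to its own device.

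**Working it through.** **Inputs**

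- Planned ITT size: N = 55 (Protocol 11.2, SAP 1.4).
- Rule: .ns is set to missing and disregarded (SAP 4.2.1).
- Number of subjects who tick a given device, k: not in the documents. Assumed at 1, 5, 11, 22, 40 and 55.
- Number of subjects with any device ticked, m: not in the documents. Assumed at 20, 30 and 40.
- Number of subjects with the question truly unanswered (.b or .n), u: not in the documents. Assumed at 0, 5 and 10.

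The plan states no usage percentage, so there is no figure of its own to reproduce.

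**Step 1. Does the rule shrink the denominator?** SAP 4.2.1 makes .ns missing, SAP 4.2 drops missing items, and Protocol 11.4 removes the subject for a variable that is missing. If each device is stored as its own variable, a subject who did not tick it is removed for that device. Read literally and together, these sections imply a non-missing denominator, but none of them states one for this table.

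**Step 2. One device under two readings.** Counting .ns as 'no' gives k/N. Dropping .ns per option gives k/k. The ratio of the second to the first is N/k.

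| k (assumed) | .ns = no: k/55 | .ns dropped: k/k | Ratio 55/k |
|---|---|---|---|
| 1 | 1.8% | 100% | 55 |
| 5 | 9.1% | 100% | 11 |
| 11 | 20.0% | 100% | 5 |
| 22 | 40.0% | 100% | 2.5 |
| 40 | 72.7% | 100% | 1.38 |
| 55 | 100% | 100% | 1 |

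For k = 0, the first reading gives 0/55 = 0% and the second gives 0/0, which is undefined. Under the second reading the result is exactly 100% for every device ticked at least once.

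**Step 3. Other denominators, with k = 11.**

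- All ITT subjects: 11/55 = 20.0%, so no inflation.
- Subjects with any device ticked: 11/20 = 55.0%, 11/30 = 36.7%, 11/40 = 27.5%.
- ITT less the truly unanswered: 11/(55 − 5) = 22.0%, 11/(55 − 10) = 24.4%.

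The same 11 ticks can therefore be reported as anything from 20% to 100%, depending on a choice that the SAP leaves open.

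**Step 4. Is connectivity a plausible tick-list?** Four devices are listed under one heading in Protocol 9.3.1. Protocol section 5 says the streamer can be paired with the microphone, TV adapter and phone adapter, so one subject may have several. The SAP itself declares .ns relevant to BC107. This makes a multi-select field likely but does not prove it.

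**The case against.** The strongest reply is that the SAP never says the percentage is taken over non-missing values. It names ITT as the analysis set for connectivity, and over 55 subjects the percentage is right. This stands in part. ITT settles who enters the analysis, but it does not cancel a rule that drops missing values within it, so the literal reading remains open.

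Four further objections have force:

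- The eCRF layout and the table guideline are not available, so it is not shown that the connectivity item carries .ns. A programmer might also handle the code sensibly.
- Usage appears as a separate field in Protocol 9.3.1, so the variable analysed may not be the device tick-list.
- SAP 3.2.3 restricts usage to devices the subject was given. For usage among recipients, leaving out a subject who never received the device is legitimate, so 11/55 is not the only defensible figure.
- Every listed device showing 100% would probably be noticed in a draft table.

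A reader might infer that the planned connectivity percentages are certain to be inflated. The documents do not support that, because both the item format and the denominator are unstated. A reader might also extend the criticism to .h, for questions hidden by a display rule. That would need a parent question whose 'none' answer hides the usage field, and no section describes one. Treating a hidden question as missing or not applicable is ordinary practice.

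**Conclusion.** SAP 4.2.1 misclassifies .ns: on a tick-list item it is a valid 'no', and the SAP orders it dropped without exception. That much is on the page. The numerical consequence is conditional on two assumptions: that the connectivity item is multi-select and exports .ns for unticked options, and that percentages use the non-missing count. If both hold, every device ticked at least once reads 100% whatever its true share, and an unticked device has no percentage. If the denominator is all ITT subjects, nothing is inflated.

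The severity is minor. The variable is additional, is summarised descriptively without a test (SAP 4.6.3), and lies outside objectives A to J. The primary endpoint, PTA4 functional gain, is numeric and does not depend on .ns. No other planned analysis is shown to depend on it.

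**What to change.** In SAP 4.2.1, remove .ns from the codes treated as missing. Recode it as No when the parent question was answered. Keep .b, .c, .d, .e, .h and .n as missing; .h may be counted separately as not applicable.

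In SAP 3.2.3, and in the specifications of Table 14A.9 and Figure 14.1.8, state two denominators: ITT subjects with the question answered, for having a device, and subjects given the device, for its usage. Show the number unanswered alongside.

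The cost is one amended SAP paragraph, a recode step in the analysis program and a line in the table specification. No new data are needed.
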